8.1 Abemaciclib

8.1.1 Description

Abemaciclib, (IUPAC: N-[5-[(4-ethylpiperazin-1-yl)methyl]pyridin-2-yl]-5-fluoro-4-(7-fluoro-2-methyl-3-propan-2-ylbenzimidazol-5-yl)pyrimidin-2-amine), or LY2835219, is a potent and selective inhibitor of CDK4 and CDK6 with IC₅₀ of 2 nM and 10 nM, respectively. It has a molecular weight of 602.7 and its chemical formula is C₂₈H₃₆F₂N₈O₃S. The half-life is 17-38 hours.

8.1.2 Storage and Stability

Abemaciclib needs to be stored in the original package. Abemaciclib needs to be kept at room temperature (approximately 15-30 degrees Celsius wherever possible).

8.1.3 Handling

Qualified personnel, familiar with procedures that minimize undue exposure to themselves and the environment, should undertake the preparation, handling, and safe disposal of the chemotherapeutic agent in a self-contained and protective environment.

8.1.4 Availability

Abemaciclib will be provided for clinical trial use as 50mg of abemaciclib with excipients in hypromellose capsules as individual patient supply packaged in bottles. Storage conditions are described in the medication label.

8.1.5 Preparation

Participants will be provided with an adequate supply of abemaciclib for self-administration at home, including instructions for administration, until at least their next scheduled study visit. Participants will receive abemaciclib on an outpatient basis. The investigator shall provide the participant with instructions for abemaciclib administration according to the protocol.

The investigator or responsible site personnel must instruct the participant or caregiver to take abemaciclib as per protocol. Abemaciclib will be dispensed to the participant by authorized site personnel only. All dosages prescribed to the participant and all dose

changes during the study must be recorded on the Dosage Administration Record CRF.

8.1.6 **Administration**

Abemaciclib is administered orally.

Compliance should be assessed by the investigator and/or study personnel at each participant visit and information provided by the participant and/or caregiver. Records of study medication used, dosages administered, and intervals between visits and the completion of the study will be captured in the Drug Accountability Form. This information must be captured in the source document at each participant visit.

8.1.7 **Ordering**

Abemaciclib will be provided to patients [REDACTED]

8.1.8 **Accountability**

The investigator, or a responsible party designated by the investigator, should maintain a careful record of the inventory and disposition of the agent using the NCI Drug Accountability Record Form (DARF) or another comparable drug accountability form. (See the NCI Investigator's Handbook for Procedures for Drug Accountability and Storage).

All drug supplies are to be used only for this protocol, and not for any other purpose.

8.1.9 **Destruction and Return**

The study drug supply will be destroyed according to the DFCI Institutional Pharmacy SOP.

9. BIOMARKER, CORRELATIVE, AND SPECIAL STUDIES

9.1 Clinical specimens collected

The following clinical specimens will be collected from patients on this study:

- a) Archival tumor tissue if available (paraffin-embedded)
- b) Blood at baseline (for collection of plasma, germline DNA and ctDNA).
- c) Blood at each time of restaging (for collecting ctDNA)
- d) Blood at C1D15, C2D1, C3D1, and at progression (for plasma)
- e) Tumor biopsy material obtained at time of study entry (if accessible disease) – both fresh frozen and formalin-fixed, paraffin-embedded

- f) Tumor biopsy material obtained at time of C2D1 (if accessible disease) – both fresh frozen and formalin-fixed, paraffin-embedded
- g) Blood at time of progression for collection of ctDNA
- h) Stool at baseline, on treatment, toxicity, and EOT/PD

Sample	Type	Visit
Archival Tissue FFPE	Tumor	Screening
Fresh Tissue FFPE and Frozen	Tumor	Screening and Cycle 2 day 1
cfDNA	Blood	Screening, Restaging, and Progression
Plasma for isolation of exosomes	Blood	Screening, C1D15, C2D1, C3D1, and Progression
Germline DNA	Blood	Screening
PBMCs	Blood	Screening, C2D1, C3D1, and Progression
Stool	Stool	Screening, Between C2D1-C3D1, grade ≥ 2 diarrhea (optional), and EOT/PD

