1.4 Exploratory objectives

To explore additional potential biomarkers in blood and tumor tissue samples that might predict response or resistance to abemaciclib.

To determine the association between genomic alterations in tumor DNA (mutations, copy number alterations, mutational burden) and RB expression and other tissue biomarkers by immunohistochemistry as well as response to abemaciclib.

To determine if there are any changes in the T-cell phenotype during exposure to abemaciclib.

To explore changes in the microbiome induced by therapy comparing stool samples collected at

baseline, during treatment, and at the time of progression. Changes in microbiome will be compared to other trial endpoints.

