3. PARTICIPANT SELECTION

3.1 Inclusion Criteria

- 3.1.1 Patients must have histologically or cytologically confirmed invasive breast cancer, which is recurrent, locally advanced, unresectable or metastatic.
- 3.1.2 Patients must have at least one lesion that is not within a previously radiated field and that is measurable per RECIST version 1.1. Bone lesions are not considered measurable.
- 3.1.3 Either the primary tumor and/or metastatic tumor must be triple-negative as defined below:
- Hormone receptor status: the invasive tumor must be ER- and PR-negative, or staining present in <1% by immunohistochemistry (IHC)
 - HER2 status: the invasive tumor must be Human Epidermal Growth Factor Receptor 2 Negative (HER2-negative) by the ASCO CAP guidelines

In cases where both primary tumor and metastatic sample(s) have been tested for ER, PR, and HER2, then the triple-negative status of the tumor should be determined from the most recent sample available.

- 3.1.4 Either the primary tumor and/or the metastatic tumor must be RB positive as defined below:
- RB status: the invasive tumor must have greater than 50% of tumor cells staining positive for RB.
- 3.1.5 Prior Chemotherapy:
- Patients may have received 1-3 prior systemic therapies for metastatic disease (note: for patients who have first developed recurrent/metastatic disease within 12 months of completing any (neo)-adjuvant therapy for triple-negative breast cancer, the (neo)-adjuvant therapy is counted as a prior line of therapy).
 - Patients must have been off treatment with myelosuppressive chemotherapy for at least 21 days or nonmyelosuppressive agents for 14 days before registration. Patients should also be adequately recovered (to baseline or grade 1) from acute toxicities of prior treatment except for residual alopecia and peripheral neuropathy.

- 3.1.6 Prior biologic therapy: Patients must have discontinued all biologic therapy at least 21 days before registration.
- 3.1.7 Prior radiation therapy: Patients may have received prior radiation therapy in either the metastatic or early-stage setting. Radiation therapy must be completed at least 7 days prior to study registration.
- 3.1.8 Patients on bisphosphonates or RANK-L inhibitors may continue receiving these therapies during study treatment. There is no washout period required between the last dose of these therapies and the start of abemaciclib.

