9.6 PBMCs

As PBMC collections were added after the study began enrolling, collections will begin with the first patient enrolled after the activation of DFCI Amendment #6.

9.6.1 Handling and shipping of PBMC specimens:

Five 10 ml EDTA tubes will be collected and processed at baseline, C2D1, C3D1, and progression for PBMCs. Fill the tubes completely and deliver to the Center for Immuno-Oncology Lab within 3-4 hours of draw at the following address:

The CIO lab staff will send reminders each week; however, please notify the lab of any planned draws so that they can staff appropriately.

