10. STUDY CALENDAR

Baseline evaluations are to be completed within 28 days prior to registration unless otherwise specified. Laboratory assessments, including pregnancy test, are to be completed within 14 days of registration. In the event that the participant's condition is deteriorating, laboratory evaluations should be repeated within 48 hours prior to initiation of the next cycle of therapy.

Assessments must be performed prior to administration of any study agent. Study assessments and agents should be administered within ± 3 days of the protocol-specified date, unless otherwise noted. Tumor assessments must be completed within ± 7 days of the protocol-specified date.

	Screening	Cycle 1		Cycle 2		Cycle 3	Cycle 4+		30 Day FUV ^k	Follow -Up
		D1	D15	D1	D28	D1	D1	D28		
Informed consent	X									
Demographics	X									
Medical history, including past lines of therapy	X									
Physical exam	X	X	X	X		X	X		X	
Vital signs ^a	X	X	X	X		X	X		X	
Height	X									
Weight	X	X		X		X	X		X	
Performance status	X	X		X		X	X		X	
Concurrent Meds	X	X	X	X		X	X		X	
AE Evaluation	X	X	X	X		X	X		X	
CBC w/diff ^f	X	X	X	X		X	X		X	
Serum chemistry ^b	X	X	X	X		X	X		X	
Serum cystatin C ^c	X	X	X	X		X	X		X	
B-HCG	X ^d									
Blood for ctDNA ^e		X				X			X	
Blood for genomic sequencing control		X								
Blood for plasma exosome analysis ^f		X	X	X		X			X	
Blood for germline DNA ^g		X								
Blood for PBMCs	X			X		X			X	
Archival tumor tissue	X									
Research stool collection and questionnaire ^m	X					X	X		X	
Research Biopsy	X			X						
EKG ^h	X									
Tumor assessments ⁱ	X				X			X	X ^{j,k}	
Abemaciclib		X-----X								
Survival Follow-up										X

Abemaciclib: 200mg po bid for 28 day cycles.

- a. Vital signs to include: diastolic and systolic blood pressure, heart rate and temperature
- b. Chemistry to include: Albumin, alkaline phosphatase, total bilirubin, bicarbonate, BUN, calcium, chloride, creatinine, glucose, potassium, total protein, SGOT [AST], SGPT [ALT], sodium.
- c. Cystatin C should be performed each time serum chemistries are performed, as abemaciclib is known to compete for tubular secretion of creatinine, causing an increase in serum creatinine which does not reflect changes in renal function. Cystatin C allows for more accurate assessment of renal function in this context.
- d. Serum pregnancy test (women of childbearing potential as defined in the eligibility section)

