- e. ctDNA to be drawn at C1D1, each restaging visit and at time of progression/30 Day FUV (Streck)
- f. Plasma to be drawn at C1D1, C1D15, C2D1, C3D1 and at time of progression/30 Day FUV (EDTA)

- g. Blood drawn at C1D1 for collection of germline DNA (Streck)
- h. EKGs to be done at Screening and if clinically indicated
- i. Tumor assessments will be performed every 2 cycles (8 weeks) for the first 6 cycles (6 months) and then every 3 cycles (12 weeks) going forward.
- j. Tumor assessments should be obtained at 30 day FUV if not done within the previous 8 weeks
- k. Follow-up survival (disease status and overall status) follow-up evaluation – a separate clinic visit is not required, this can be done over the phone every six months.
- l. 30 Day FUV to be completed within 30 days of last dose of abemaciclib
- m. Research stool collection to occur at baseline, between C2D1 and C3D1, at the time of grade ≥ 2 diarrhea, and at the end of treatment or progression, whichever occurs first.

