13.5 Analysis of Exploratory Endpoints

Descriptive statistics will be used to characterize any types of biomarkers discovered in correlative work, T-cell phenotypes via serial PBMCs blood draws (prior to receiving therapy, while on therapy, and at the time of progression), any changes in the serial microbiome collection, and its correlation with participant outcomes.

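### The PBMC baseline is drawn at screening and is not tied to the prior-therapy washout, so for some patients the T-cell change from baseline could include recovery from earlier treatment

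*Combined protocol and SAP*

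**What the plan says.** **Objective and analysis.** Section 1.4 gives the exploratory aim: "To determine if there are any changes in the T-cell phenotype during exposure to abemaciclib". Section 13.5 plans descriptive statistics on serial PBMC draws taken "prior to receiving therapy, while on therapy, and at the time of progression". It states no adjustment for time since prior therapy or since the last abemaciclib dose.

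**PBMC draws.** The table in section 9.1 gives "Screening, C2D1, C3D1, and Progression". Section 9.6.1 says "Five 10 ml EDTA tubes will be collected and processed at baseline, C2D1, C3D1, and progression for PBMCs" and does not define the baseline day. Section 9.6 limits collection to patients enrolled after Amendment 6 was activated. In the section 10 calendar, the row "Blood for PBMCs" is marked under Screening, C2D1, C3D1 and the 30 Day FUV. It has no mark at C1D1 and no footnote.

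**Windows.** Section 10 says "Baseline evaluations are to be completed within 28 days prior to registration unless otherwise specified" and sets a 14-day limit for laboratory assessments. It does not say which limit governs PBMCs. Section 3.1.5 says "Patients must have been off treatment with myelosuppressive chemotherapy for at least 21 days or nonmyelosuppressive agents for 14 days before registration". Section 3.1.6 asks for 21 days off biologic therapy, again counted to registration.

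**Last draw.** Calendar footnote l says "30 Day FUV to be completed within 30 days of last dose of abemaciclib". Footnotes e and f treat progression and the 30 Day FUV as one draw for ctDNA and plasma. Nothing does so for PBMCs.

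**The concern.** The trial has one arm, so the T-cell objective is read from change within each patient. A change from baseline describes exposure to abemaciclib only so far as the baseline reflects the patient's state just before the first dose. All patients are pretreated (section 3.1.5 allows 1 to 3 prior systemic therapies). Screening and washout are both counted back from registration, and no rule orders the PBMC draw relative to the last prior dose. If the sample is taken while earlier therapy is still being given or has just stopped, any immune recovery before C1D1 falls between the baseline and C2D1 samples and would be read as part of the on-treatment change. A baseline sample cannot be redrawn once treatment starts.

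A second, separate matter is the final sample. The text places it at progression and the calendar at the 30 Day FUV. Depending on which is followed, it may be taken with drug on board, after the drug has cleared, or after new therapy has begun.

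**Working it through.** The documents give no sample size, power or effect size for the PBMC analysis, so there is no planned figure to reproduce. The check is date arithmetic, half-life arithmetic and a reading of the calendar rows.

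**1. Where the research bloods sit in the section 10 calendar**

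| Row | Marked at |
|---|---|
| PBMCs | Screening, C2D1, C3D1, 30 Day FUV |
| ctDNA | C1D1, C3D1, 30 Day FUV |
| Plasma | C1D1, C1D15, C2D1, C3D1, 30 Day FUV |
| Germline DNA | C1D1 |

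The section 9.1 table labels the ctDNA, plasma and germline baselines as Screening too, although the calendar and footnotes e to g put them at C1D1. That table therefore uses the word loosely, and the calendar row is the stronger evidence for PBMCs.

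**2. Interval from last prior dose to the baseline draw**

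Let W be the minimum washout (sections 3.1.5 and 3.1.6) and d the number of days by which the draw precedes registration. For a patient exactly at minimum washout, the interval is W − d, with d running from 0 to the length of the window.

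| Prior therapy | W | 28-day window | 14-day window |
|---|---|---|---|
| Myelosuppressive | 21 | 21 − 28 = −7 to +21 | 21 − 14 = +7 to +21 |
| Biologic | 21 | −7 to +21 | +7 to +21 |
| Nonmyelosuppressive | 14 | 14 − 28 = −14 to +14 | 14 − 14 = 0 to +14 |

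A negative value means the baseline is drawn before the last prior dose. Under either window the draw can fall inside the washout. A longer actual washout shifts every range later by the same number of days.

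**3. The same interval with the draw at C1D1**

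Section 4.1 requires registration before protocol therapy, so C1D1 does not precede registration (d ≤ 0). The interval is then at least W: 21 days for myelosuppressive and biologic agents, 14 days for nonmyelosuppressive agents.

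**4. Which comparisons use the baseline**

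Baseline to C2D1 and baseline to C3D1 both do. C2D1 to C3D1 does not, so baseline timing cannot affect it, but it misses any change during cycle 1.

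**5. The last draw**

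Section 8.1.1 gives a half-life of 17 to 38 hours. The fraction remaining after t hours is 0.5^(t / half-life).

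- Five half-lives: 5 × 17 / 24 = 3.5 days to 5 × 38 / 24 = 7.9 days.
- Day 3 (72 h): 5% to 27% remaining.
- Day 7 (168 h): 0.1% to 4.7% remaining.
- Day 30 (720 h): 720 / 38 = 18.9 to 720 / 17 = 42.4 half-lives, under 0.001% remaining.

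A draw more than about 8 days after the last dose is essentially off drug. A draw on the day progression is found may still be on drug. Section 5.4 restricts other anticancer therapy only during study treatment, so new therapy could precede a late draw.

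**The case against.** The strongest reply is that overlap with washout is possible, not planned. Washout is a minimum and the screening window is an outer limit. A patient at exact minimum washout who is sampled on the day of registration is already 21 or 14 days clear. The calendar's Screening column does not in itself mean day −28: the research biopsy sits there too, yet section 3.1.17 holds it to 7 days before C1D1. This stands as far as it goes, but it also shows that the protocol can set a tighter limit when it wants one, and it sets none for PBMCs.

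A reader might infer that every patient is affected, since all are pretreated. The documents do not support that. The number of prior lines says nothing about time since the last dose, and under section 3.1.5 a line may be (neo)adjuvant therapy finished months earlier.

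A reader might also infer that a C1D1 sample is the only reference that could isolate the drug effect. That is too strong. The C2D1-to-C3D1 contrast does not need a baseline, recovery may continue after C1D1, and one arm cannot separate drug from time.

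On the last draw, a reader might infer a planned off-drug sample. Sections 9.1, 9.6.1 and 13.5 all say progression. The calendar has no progression column, and its visit falls on any day up to day 30. The likeliest explanation is a missing footnote. Off-drug status would in any case touch only that sample, which section 13.5 lists apart from the on-therapy draws.

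Finally, the documents give no recovery time and no expected effect of prior therapy on the core markers in section 9.6.2. The harm is plausible but unquantified. That stands.

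**Conclusion.** The point holds as a low-cost improvement. As written, the plan permits a PBMC baseline from 7 days (myelosuppressive or biologic) or 14 days (nonmyelosuppressive) before the last prior dose. If the 14-day laboratory window applies, the earliest draw is 7 days after that dose or on the same day. For patients near the minimum washout, recovery between screening and C1D1 could be counted in the baseline-to-C2D1 and baseline-to-C3D1 changes. Patients long off therapy and the C2D1-to-C3D1 contrast are unaffected.

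The ranges assume exact minimum washout and use of the full window. How many patients come near that, and how large any bias would be, cannot be computed: the documents give no distribution of time since prior therapy and no number of patients with PBMCs. The consequence is confined to an exploratory, descriptive objective in patients enrolled after Amendment 6. The response-rate endpoint, the two-stage rule and the secondary endpoints are untouched.

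The mismatch between progression and the 30 Day FUV is a separate inconsistency to be reconciled. It does not show that the final sample is always off drug.

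**What to change.** 1. Move the baseline PBMC draw from Screening to C1D1 before the first dose, in the calendar and in sections 9.1 and 9.6.1. This joins the research bloods already drawn that day and secures at least 21 or 14 days since prior therapy. It does not exclude recovery that continues after C1D1.
2. Record days from last prior therapy to the baseline draw, and report them with the T-cell results. For patients already sampled at screening, this is the part that can still be done.
3. Reconcile the calendar's 30 Day FUV mark for PBMCs with the progression draw in sections 9.1, 9.6.1 and 13.5, for example with a footnote like those for ctDNA and plasma. At that draw, record days since the last abemaciclib dose and any new anticancer therapy.
4. State in section 13.5 that baseline to C2D1 and C3D1 is the exposure contrast, and describe the final sample separately.

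Cost: wording changes and a few recorded dates. The number of samples and visits stays the same. The downside is about 50 mL more blood at C1D1 (five 10 mL tubes), moved from screening.

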9.2 Archival Tissue Specimens

9.2.1 Collection of Archival specimen(s)

Archival tissue will be collected at screening to determine tumor RB status and potential eligibility for the trial. RB status will be determined using immunohistochemistry on formalin-fixed, paraffin embedded tissue.

The staining will be done using Rb antibody clone G3-245 using a protocol developed in the BWH clinical immunohistochemistry laboratory (CLIA conditions). A BWH pathologist ([name]) will review the stained slides and results will be reported to the study team. To be considered RB positive, the invasive tumor must have greater than 50% of tumor cells staining positive for RB. The expected turnaround time between receipt of tissue (slides or blocks) and delivery of the staining result is expected to be approximately 7-14 days.

We are requesting that 1 FFPE block or 15 unstained slides and 1 representative H&E stained slide containing tumor tissue be provided from each patient's definitive surgery or metastatic biopsy. The tissue requisition provided in (Appendix D) should be completed and submitted

with the tissue specimen and pathology report. If the archival specimen is from an outside hospital, please ensure the outside institutions pathology report is provided.

In addition to screening potentially eligible patients for RB-positivity by performing immunohistochemistry on archival tissue, we will also ask screened patients to consent for further studies on archival tissue when available. These studies will include (but will not be limited to) assessment of genomic and transcriptomic predictors of response to abemaciclib, as well as description of the correlations between RB-positivity by IHC and gene expression signatures in the tumor. In those patients that provide informed consent for this, we will perform both DNA and RNA extraction from the formalin-fixed, paraffin embedded archival tumor tissue available.

9.2.2 Handling of Archival specimen(s)

Once blocks/slides are received, RNA will be extracted from archival tumor tissue (**preferably the primary breast tumor**). This RNA will then be subjected to analysis of gene expression by Affymetrix microarray and/or using the Nanostring nCounter platform. Tumors will be classified according to published algorithms to determine their individual TNBC subtype. We expect that the majority (but not all) of the RB-positive tumors will fall into the “Luminal Androgen Receptor” or “Mesenchymal Stem Like” subtypes, and as an exploratory analysis will determine if tumors within this subtype have a higher rate of response to abemaciclib.

Additionally, in patients who consent, RNA extracted will be used to quantify the expression of several genes, including (but not limited to) those used to classify tumors into PAM50 subtypes[18], those identifying specific TNBC subtypes [19][8], and those that contribute to a signature of RB proficiency or deficiency. This will allow us to depict the landscape of gene expression for all tumors in this study, and also to determine in an exploratory fashion the correlation (or lack thereof) between RB positivity by IHC and “Rb-proficiency” by gene expression. DNA extracted will be stored with a view to performing whole exome sequencing. This will allow a depiction of the landscape of genomic alterations of all patients screened for the study, and specifically allow for an exploratory comparison of mutational profiles in tumors that do and do not stain positively for RB.

